8.3.2 Overdose

An overdose is defined as the accidental or intentional ingestion or infusing of any dose of a product that is considered BOTH excessive AND medically important. All occurrences of overdose must be reported as an SAE. These AEs will be monitored as instructed in the schedule of events and as clinically indicated.

9. Statistical Considerations

9.1 *General Considerations*

For the purposes of this protocol and all analyses, a cycle of treatment is defined as 28 days.

9.2 *Analysis Population*

Intention to treat (ITT) population: The ITT population includes all subjects who are enrolled in the study.

Safety Population: The safety population includes all subjects who have received at least 1 dose of PIO.

Per-protocol Population: The per-protocol population includes all subjects who are enrolled, receive at least one dose of study drug, and have no major protocol violations that could be expected to impact response data, such as: failure to satisfy one or more eligibility criteria, administration of other anti-cancer therapy concurrent with study drug, and administration of incorrect study drug dose. Major protocol violations will be finalized and documented prior to final data analysis.

9.3 Study Endpoints

The primary endpoint of this study is to determine safety and efficacy of PIO administered in combination with TKI. Therefore, description of AEs in subjects receiving the combination of PIO and TKI will be collected. AEs will be graded according to the CTCAE v.4.03 assessed through scheduled assessment and subject reported diary. Efficacy is determined by the proportion of subjects who achieve and maintain < MR^{4,5} using blood qRT-PCR for *BCR-ABL1* obtained monthly while on PIO and TKI.

Secondary endpoint of the study is to determine the proportion of subjects who lose MMR following discontinuation of PIO and TKI using blood qRT-PCR for *BCR-ABL1* obtained monthly for the first 3 months then quarterly.

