9.4 Determination of Sample Size

Previous reports suggest that PIO is well tolerated at the doses of 30 and 45 mg [47]. Under Simon's optimal two stage design with a 5% significance level and 80% power, assuming a lower boundary of interest in the response rate of 20% and an upper boundary of interest in the response rate of 50%, a total of 24 evaluable subjects are required for the evaluation of the primary endpoint; 9 in Stage 1 and an additional 15 in Stage 2. If $\leq 2/9$ evaluable subjects in Stage 1 maintain MMR after second-TKI discontinuation or ≥ 2 subject develop \geq grade 3 cardiac toxicity then the study will terminate, otherwise the study shall continue as planned and enrollment of an additional 15 subjects shall continue into Stage 2. If, at the final analysis, less than 9 of 24 evaluable subjects in both Stage 1 and 2 maintain MMR then it will be concluded that the combination of PIO and TKI does not deserve further investigation. After adjusting for 8% drop out rate, the actual required sample size will be 26 subjects. Therefore, the total sample size of the study will be 26 subjects.

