9.5 Safety and Efficacy Analysis

All subjects receiving at least 1 dose of study drug will be considered evaluable for safety. Listings of laboratory test results will also be generated, and descriptive statistics summarizing the changes in laboratory tests over time will be presented. Exposure to study drug over time will also be summarized. The AE incidence rates, as well as the frequency of occurrence of overall toxicity, categorized by toxicity grades (severity) will be described. The number of subjects that has reappearance of *BCR-ABL1* will be described. Descriptive statistics that will summarize the changes in *BCR-ABL1* testing over time will be presented. Loss of MMR is defined as a *BCR-ABL1* $>0.1\%$ by qRT-PCR confirmed within a week and associated with a rise in the titer on a confirmatory test obtained 4 weeks later (ELN definition). For the primary and secondary efficacy endpoints, subgroup analyses will be performed by baseline potential prognostic factors. Subgroups will include: age, gender, race, underlying diagnosis, and other disease-related prognostic factors (disease status).

9.6 *Interim Analysis*

An interim analysis is planned after 9 subjects have been enrolled and their results have been obtained. This interim analysis will focus on efficacy as discussed in section 9.4 and safety. If grade 3-4 toxicity is observed at any moment in 2 subjects, the trial will be put on hold and no further subjects will be enrolled until analyses of these cases is complete and reviewed by the data safety monitoring board (**DSMB**).

9.7 *Protocol Deviations and Violations*

To be protocol-compliant, a subject must not have any major protocol deviations during the study period. Protocol deviations will be identified prior to final analysis and will be listed by treatment group in the clinical study report.

10. Quality Control and Quality Assurance and Study Monitoring

The investigator is responsible for performing quality control and assurance checks. Before enrolling any subjects into this study, the investigator will review the protocol, the CRFs and instructions for their completion, the procedure for obtaining informed consent, and the procedure for reporting AEs with all personnel listed on the delegation of authority and FDA1572. The investigator will evaluate the conduct of the trial at least once monthly and perform the following:

- Review information recorded in the CRFs and verify against source documents

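### Section 9.3 labels on-treatment MR4.5 as primary efficacy and post-stop MMR as secondary, but the trial is sized and decided on post-stop MMR

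*Combined protocol and SAP*

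**What the plan says.** Section 9.3 gives a joint primary endpoint of safety and efficacy. On efficacy it states: "Efficacy is determined by the proportion of subjects who achieve and maintain" a response below MR4.5, by monthly PCR during the combination. It continues: "Secondary endpoint of the study is to determine the proportion of subjects who lose MMR following discontinuation of PIO and TKI".

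Section 9.4 states that "a total of 24 evaluable subjects are required for the evaluation of the primary endpoint". Its Stage 1 rule stops the study if two or fewer of nine "evaluable subjects in Stage 1 maintain MMR after second-TKI discontinuation". Its final rule is negative if fewer than 9 of 24 evaluable subjects maintain MMR. Otherwise, after Stage 1, "enrollment of an additional 15 subjects shall continue into Stage 2".

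On analysis sets, 9.2 says "The ITT population includes all subjects who are enrolled in the study" and "The per-protocol population includes all subjects who are enrolled, receive at least one dose of study drug, and have no major protocol violations". Neither set is assigned to the 9.4 count. The only definition of evaluable is in 9.5 and concerns safety: "All subjects receiving at least 1 dose of study drug will be considered evaluable for safety".

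On timing, 3.1 ends participation after two years off TKI or at loss of MMR. Section 9.6 places the interim once nine subjects are enrolled and their results are in. Neither section says at what time after the stop a subject counts as having maintained MMR.

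**The concern.** On-treatment MR4.5 and off-treatment MMR are measured in different periods and at different thresholds. In 3.1 the first is the condition for attempting the second stop, so it cannot show whether remission holds off drug. As written, two variables could each be reported as the primary efficacy result, and only the one labelled secondary has a sample size and a go/no-go rule. In an open-label single-arm trial, a clear prior statement of the primary endpoint is the main protection against choosing after the data are seen.

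The count that decides the trial also lacks a stated time and a defined denominator, and its Stage 1 cut-off differs between sections.

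**Working it through.** **1. Which outcome each section uses**

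| Place | Outcome |
|---|---|
| Synopsis objectives and endpoints; 2.1; 3.2 | MMR kept after the second stop |
| 2.2 hypothesis | same, at least 50% |
| 1.6 / 1.3 | success of a second stop, 20% / 25% |
| 9.4 rules; synopsis rules; 12.4 (Stage 1 only) | same |
| 9.3 primary efficacy | MR4.5 on the combination |
| 9.3 secondary | loss of MMR after stopping |

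Only 9.3 departs. Section 3.2 lists post-stop MMR as the sole efficacy endpoint, without a primary or secondary label.

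**2. The plan's own rule.** With 9.4 as written (continue at 3 or more of 9; success at 9 or more of 24):

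P(success | p) = Σ(x = 3 to 9) P(X₁ = x) · P(X₂ ≥ 9 − x), with X₁ ~ Bin(9, p) and X₂ ~ Bin(15, p).

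This gives 0.029 at 20%, 0.100 at 25% and 0.866 at 50%, so the rule meets 5% and 80% for 20% against 50%. An exact search puts the Simon optimal design for those inputs at 18 subjects, not 24. That is a separate matter and does not affect this point. For dropout, 24/0.92 = 26.1, given as 26.

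**3. The 20% and 50% do not carry over to MR4.5.** In the institutional data in 1.3, 4 of 7 evaluable subjects (57%; exact 95% interval 18% to 90%) went below MR4.5 after restarting imatinib, before any pioglitazone. At a true 57% the 9.4 rule would declare success with probability 0.95. This is indicative only: n is 7, and 9.3 also requires the response to be maintained.

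**4. Time point.** Assumptions: 25% durable rate; exponential losses with a 4-month median, taken from the site's first discontinuations because the documents give no timing for a second stop; final count at full follow-up. The share of losses seen by month t is f = 1 − 0.5^(t/4). The apparent rate is a = 0.25 + 0.75(1 − f). Stage 1 passes with P(Bin(9, a) ≥ 3), and expected enrolment is 9 + 15 × that probability.

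| Read | f | a | Stage 1 pass | Expected enrolment | Overall success |
|---|---|---|---|---|---|
| 12 months | 0.875 | 0.344 | 0.65 | 18.7 | 0.11 |
| 24 months | 0.984 | 0.262 | 0.43 | 15.5 | 0.10 |
| All losses seen | 1 | 0.250 | 0.40 | 15.0 | 0.10 |

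**5. Stage 1 cut-off.** Section 9.4 stops at two or fewer of nine; the synopsis and 12.4 stop at fewer than two. At a 25% rate with all losses seen, P(Bin(9, 0.25) ≥ 3) = 0.40 and P(Bin(9, 0.25) ≥ 2) = 0.70. All figures in step 4 use the 9.4 version.

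**6. Denominator.** If only subjects who stop TKI count, 24 of 26 is 92%. With an assumed share q reaching discontinuation, P(Bin(26, q) ≥ 24) is 0.65 at 92%, 0.51 at 90% and 0.03 at 75%. At 75%, 24/0.75 = 32 enrolled would be needed on average.

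**7. Calendar.** Assume even accrual of 26 over 24 months and that all of the first nine reach discontinuation. The ninth enters at 9/(26/24) = 8.3 months. Add 6 to 12 months on the combination, then the landmark:

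- 12-month read: 26 to 32 months.
- 24-month read: 38 to 44 months.

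Both fall after the 2-year accrual. If Stage 2 waits, add 13.8 to 15.7 months for 15 to 17 subjects, then 18 to 24 months (12-month read) or 30 to 36 months (24-month read). The final result comes at about months 58 to 72 or 82 to 96, against the 60 planned in 5.4.

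**The case against.** The strongest reply is that the intent is plain. Every section except 9.3 uses post-stop MMR and no go/no-go decision depends on MR4.5, so the harm is confined to labelling and reporting. This stands as far as it goes: a reader might infer that the deciding variable is in doubt, and the documents do not support that. But 9.3 is the section that formally defines the endpoints, and it contradicts 9.4 outright.

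Two other strong readings fail:

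- **Futility stop largely lost.** A reader might infer this from the missing time point. It would need a read when only half or three quarters of losses have occurred, about 4 or 8 months under the assumption above, and no section suggests such a read. The two years off TKI in 3.1, the three years for the last subject in 5.4 and the wording of 9.6 all point to full follow-up. The gap is that nothing ties the count to it. The synopsis Kaplan-Meier analysis copes with incomplete follow-up but does not feed the binary rule.
- **Large power loss from counting everyone enrolled.** The efficacy objective (synopsis and 2.1) is confined to subjects who achieve or maintain MR4.5 on at least 6 months of the combination, which points to those who stop TKI. The plan also gives no rule for a 26-subject denominator. What remains is that evaluable is undefined for efficacy and that 26 may not yield 24.

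**Conclusion.** The endpoint contradiction is certain, rests on no assumption and must be corrected: 9.3's primary efficacy measure has no null rate, target or decision rule, while the variable that decides the trial is called secondary.

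The time point and the analysis set are secondary clarifications. A 12-month Stage 1 read weakens the futility stop moderately (pass 0.65 against 0.40) and a 24-month read hardly at all (0.43). Overall false success stays at 0.10 to 0.11. These figures depend on the assumed 25% rate, the assumed loss pattern and the 9.4 cut-off. The unreconciled cut-off alone moves the Stage 1 pass from 0.40 to 0.70, more than a 12-month read does. The chance of obtaining 24 evaluable subjects depends wholly on a share that the documents do not give.

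**What to change.** In 9.3, make the proportion maintaining MMR after the second TKI discontinuation the primary efficacy endpoint and move on-treatment MR4.5 to secondary. In the same edit:

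- **Time.** Tie the count in 9.4, 9.6 and 12.4 to one stated time after the stop, and state the 20% and 50% at that time. The two-year follow-up in 3.1 is the natural candidate.
- **Denominator.** Define evaluable for the efficacy count. If it means subjects who stop TKI, note that 24 of 26 needs about 92% to reach that point, and also report the all-enrolled proportion.
- **Cut-off.** Reconcile the Stage 1 rule in 9.4 with the synopsis and 12.4.
- **Calendar.** Reconcile the Stage 1 read with the accrual and duration in 5.4, since 9.4 makes Stage 2 enrolment depend on it.

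The endpoint change costs only wording. A 12-month read uses a PCR already scheduled. A 24-month read needs a stated visit window, because the schedule in 3.1 can be read as months 15, 21 and 27 or as months 18 and 24. The real cost of a long landmark is a later Stage 1 read, with a possible accrual pause or a longer study.

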9.4 Determination of Sample Size

Previous reports suggest that PIO is well tolerated at the doses of 30 and 45 mg [47]. Under Simon's optimal two stage design with a 5% significance level and 80% power, assuming a lower boundary of interest in the response rate of 20% and an upper boundary of interest in the response rate of 50%, a total of 24 evaluable subjects are required for the evaluation of the primary endpoint; 9 in Stage 1 and an additional 15 in Stage 2. If $\leq 2/9$ evaluable subjects in Stage 1 maintain MMR after second-TKI discontinuation or ≥ 2 subject develop \geq grade 3 cardiac toxicity then the study will terminate, otherwise the study shall continue as planned and enrollment of an additional 15 subjects shall continue into Stage 2. If, at the final analysis, less than 9 of 24 evaluable subjects in both Stage 1 and 2 maintain MMR then it will be concluded that the combination of PIO and TKI does not deserve further investigation. After adjusting for 8% drop out rate, the actual required sample size will be 26 subjects. Therefore, the total sample size of the study will be 26 subjects.

9.5 Safety and Efficacy Analysis

All subjects receiving at least 1 dose of study drug will be considered evaluable for safety. Listings of laboratory test results will also be generated, and descriptive statistics summarizing the changes in laboratory tests over time will be presented. Exposure to study drug over time will also be summarized. The AE incidence rates, as well as the frequency of occurrence of overall toxicity, categorized by toxicity grades (severity) will be described. The number of subjects that has reappearance of *BCR-ABL1* will be described. Descriptive statistics that will summarize the changes in *BCR-ABL1* testing over time will be presented. Loss of MMR is defined as a *BCR-ABL1* $>0.1\%$ by qRT-PCR confirmed within a week and associated with a rise in the titer on a confirmatory test obtained 4 weeks later (ELN definition). For the primary and secondary efficacy endpoints, subgroup analyses will be performed by baseline potential prognostic factors. Subgroups will include: age, gender, race, underlying diagnosis, and other disease-related prognostic factors (disease status).

9.6 *Interim Analysis*

An interim analysis is planned after 9 subjects have been enrolled and their results have been obtained. This interim analysis will focus on efficacy as discussed in section 9.4 and safety. If grade 3-4 toxicity is observed at any moment in 2 subjects, the trial will be put on hold and no further subjects will be enrolled until analyses of these cases is complete and reviewed by the data safety monitoring board (**DSMB**).

9.7 *Protocol Deviations and Violations*

To be protocol-compliant, a subject must not have any major protocol deviations during the study period. Protocol deviations will be identified prior to final analysis and will be listed by treatment group in the clinical study report.

10. Quality Control and Quality Assurance and Study Monitoring

The investigator is responsible for performing quality control and assurance checks. Before enrolling any subjects into this study, the investigator will review the protocol, the CRFs and instructions for their completion, the procedure for obtaining informed consent, and the procedure for reporting AEs with all personnel listed on the delegation of authority and FDA1572. The investigator will evaluate the conduct of the trial at least once monthly and perform the following:

- Review information recorded in the CRFs and verify against source documents
- Review data for safety information and to identify missing data
- Review protocol violations, out-of-range data, and other data inconsistencies

This study will be monitored by the DSMB Winship Committee.

11. Ethical Conduct of the Study

This study will be conducted in accordance with the ethical standards that have their origin in the Declaration of Helsinki and that are consistent with GCP guidelines and the applicable regulatory requirements.

11.1 *Institutional Review Boards Approval*

The protocol and the informed consent document must have the initial and at continuing approvals of the IRB. The signed IRB approval letter must identify the documents approved (i.e., list the investigator's name, the protocol number and title, the date of the protocol and informed consent document, and the date of approval of the protocol and the informed consent document). Any advertisements used to recruit subjects should also be reviewed by the IRB.

11.2 *Subject Information and Consent*

The study informed consent form will follow regulations that provide protection for human subjects in clinical investigations and describe the general requirements for informed consent. The informed consent

document will contain all of the elements of the informed consent specified in the regulations. Nothing in this protocol or the regulations is intended to limit the authority of a physician to provide emergency medical care under applicable regulations. In addition, regulatory agencies will be granted permission to conduct inspections and review records pertaining to this clinical investigation.

11.3 *Subject Confidentiality*

Throughout the course of the study, all private information will be kept securely using password protected computer terminals. Access to the data will be on a need to know basis, therefore, only those investigators listed in the protocol will have access to the data. A high premium will be placed on ensuring that identifying information is not made available to staff engaged in routine care of the subject unless necessary for the safe performance of their duties. For this reason, all research-related samples and clinical data will be de-identified using assigned study-specific registration numbers for such non-standard of care procedures as much as possible.

The investigator agrees to keep all information in strict confidence and to request similar confidentiality from his/her staff and the IRB. Study documents will be stored appropriately to ensure their confidentiality. The information provided to the investigator may not be disclosed to others without direct written authorization, except to the extent necessary to obtain informed consent from subjects who wish to participate in the trial.

11.4 *Data Safety Monitoring Committee*

Subject safety, study efficacy and compliance will be reviewed at the weekly Hematology working group meetings. The Data and Safety Monitoring Committee (**DSMC**) of the Winship Cancer Institute will also oversee the conduct of this study. This committee will review pertinent aspects of study conduct including subject safety, compliance with protocol, data collection and efficacy. The committee will review the charts of 10% of subjects enrolled to the study and two of the first 5 subjects entered to the study. The Committee reserves the right to conduct additional audits if necessary. The PI or designee is responsible for notifying the DSMC about the accrual of subjects when the first 5 have been entered to the study. The PI or designee will also notify the DSMC of study status within 2 months before the next scheduled review is due.

12. Data Handling and Record Keeping

12.1 *Case Report Forms and Study Records*

Study-specific CRFs will be made available for the conduct of this study. Study data, contained in source documentation, will be entered into the CRFs for all subjects enrolled in the study. All pertinent data records will be maintained as required after completion or termination of the study.

12.2 *Source Documents*

The investigator agrees that qualified representatives of the sponsor and regulatory agencies will have the right, both during and after this study, to conduct inspections and to audit and review medical records pertinent to the clinical study as permitted by the regulations. Subjects will not be identified by name in

any reports stemming from the study, and confidentiality of information in medical records will be preserved. The confidentiality of the subject will be maintained unless disclosure is required by regulations.

